ULN	upper limit of normal
US	United States of America
WHO	World Health Organization

4. Introduction

This statistical analysis plan (SAP) details comprehensive, technical specifications of the statistical analyses of the efficacy and safety data outlined and/or specified in the protocol amendment #2 dated 06 Dec 2017 of Study UBR-MD-04. Specifications of tables, figures, and data listings are contained in a separate document. The SAP for health economics and outcomes research (HEOR) data will be prepared separately.

This document is organized into 3 main sections:

1. Study overview
2. [Statistical Methodology and Study Endpoints](#)
3. [Data Handling and Analysis Conventions](#)

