4.1 Study Design Summary

Structure: Multicenter, randomized, open-label, 52-week extension study; randomization to the ubrogepant arms (50 and 100 mg) will be blinded.

Duration: 52 weeks

Study Treatment Groups: usual care, ubrogepant 50 mg, or ubrogepant 100 mg

Controls: Not applicable

Dosage/Dose Regimen: Patients randomized to either of the ubrogepant arms will treat up to 8 migraine attacks (of any pain severity) every 4 weeks at home for a total 1 year. Patients have the option to take a second dose of ubrogepant if the patient has either a nonresponding migraine or a migraine recurrence. The second dose of ubrogepant will be identical to the first dose.

Patients randomized to the usual-care arm will be instructed to treat their migraine with medications that they routinely use to relieve a migraine attack.

Randomization: [REDACTED] Patients will be randomized (1:1:1) to 1 of the following 3 treatment groups: usual care, ubrogepant 50 mg, or ubrogepant 100 mg. The study is open-label; however, randomization to the ubrogepant arms (50 and 100 mg) will be blinded.

[REDACTED]

Number of Participants: Approximately 1200 patients will be randomized (400 patients per arm) from approximately 200 centers in the United States.

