5.1.1.1.3 Statistical Methodology

The methodologies defined below apply as specified to individual endpoints defined in this SAP. All statistical tests will be 2-sided hypothesis tests performed at the 5% level of significance for main effects. All confidence intervals will be 2-sided 95% confidence intervals, unless stated otherwise.

Table 5-2 Statistical Methodology

Methodology	Description
M1 Categorical counts	
 • Number of participants in individual categories 
 ○ Participants with ≥ 1 qualifying event counted once per individual category
M2 Categorical descriptives	
 • Number and percentage of participants in individual categories 
 ○ Participants with ≥ 1 qualifying event counted once per individual category • N1 if proportion denominator \neq number of participants in the population (standard percentage denominator) 
 ○ N1 = participants with non-missing baseline value
M3 PCS descriptives	
 • Number and percentage of participants meeting potentially clinically significant (PCS) criteria 
 ○ Participants with ≥ 1 qualifying event counted once per PCS category • Percentage denominator = number of participants with all non-missing non-PCS baseline and ≥ 1 non-missing postbaseline assessment 
 ○ Unevaluable assessments considered missing
M4 Shift analysis	
 • Number and percentage of participants in individual baseline and postbaseline categories • Percentage denominator = number of participants in individual baseline categories • N1 = participants with non-missing values at both baseline and the specified postbaseline analysis visit
M5 Continuous descriptives	
 • N1, mean, standard deviation (SD), median, minimum, maximum • N1 = participants with non-missing value
M6 CFB descriptives	
 • Continuous descriptives for baseline, postbaseline, and change from baseline (CFB) values • N1 = participants with non-missing values at both baseline and the specified postbaseline analysis visit

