5.1.1.4.2 Adverse Events

The following adverse event (AE) terms are defined:

Table 5-19 AE Terms

Term	Description
Treatment-emergent	An event that initially occurs or increases in intensity on or after the initial dose of treatment of the lead-in study. An event that occurs after Visit 16 for participants with Visit 16, or more than 30 days after the last visit or last treatment, whichever is later, for participants without Visit 16 will not be considered as treatment-emergent.

Term	Description
On-therapy	An event where: 
 • Treatment start date of the lead-in study \leq event start date \leq Visit 16 for participants with Visit 16, or within 30 days after the last visit or last treatment, whichever is later, for participants without Visit 16

AEs, encompassing abnormalities and surgeries reported as occurring after the Screening Visit, will be coded using MedDRA version 20.1 or newer. Unique participants reporting AEs in the following AE categories will be summarized by treatment group for the Safety Population as follows:

Table 5-20 AE Summaries

Parameter	Description	Timing	Methodology
Overall summary	Overall summary only for the following categories: 
 • Treatment-emergent AEs (TEAEs) • Treatment-related TEAEs • On-therapy serious adverse events (SAEs) • Deaths • AEs leading to discontinuation Subgroup analyses by Cardiovascular Risk Category and by renal function class	From randomization date to Visit 16 for participants with Visit 16, or within 30 days after last visit or last treatment, whichever is later, for participants without Visit 16	Categorical descriptives

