TEAEs	Summary by 
 • SOC and PT for all participants and by subgroup analyses: 
 ○ by Sex ○ by Age Group <40 vs \geq40 ○ by Age Group <65 vs \geq65 ○ by Race White vs All other races ○ by cardiovascular risk category ○ by renal function class • SOC and PT for concomitant medication classes used by at least 10% of participants in at least one treatment group • SOC, PT, and AE onset time intervals 
 ○ <3 months ○ \geq3 and <6 months ○ \geq6 and <9 months ○ \geq9 and <12 months ○ \geq12 months • SOC, PT, and average number of migraine attacks treated with study treatment per month 
 ○ \geq2 ○ \geq4 ○ \geq6 	From randomization date to Visit 16 for participants with Visit 16, or within 30 days after last visit or last treatment, whichever is later, for participants without Visit 16	Categorical descriptives

Parameter	Description	Timing	Methodology
	
 ○ ≥8 • SOC, PT, and severity • SOC, PT, and causal relationship to the study treatment • Type (Mild, Moderate, Severe, related, not related) • SOC and PT for TEAEs occurring in ≥ 2% of participants in any ubrogapant treated dose group (and greater than placebo) 		
Common TEAEs	Summary by PT 
 • Includes TEAEs occurring in ≥ 2% of participants in any treatment group 	From randomization date to Visit 16 for participants with Visit 16, or within 30 days after last visit or last treatment, whichever is later, for participants without Visit 16	Categorical descriptives
On-therapy SAEs ¹	Overall summary and by PT	From randomization date to Visit 16 for participants with Visit 16, or within 30 days after last visit or last treatment, whichever is later, for participants without Visit 16	Categorical descriptives
On-therapy fatal SAEs	Participants who report On-therapy fatal SAEs will have their fatal SAEs and all AEs listed	From randomization date to Visit 16 for participants with Visit 16, or within 30 days after last visit or last treatment, whichever is later, for participants without Visit 16	Categorical descriptives
AEs leading to discontinuation ²	Overall summary and by PT	From randomization date to Visit 16 for participants with Visit 16, or within 30 days after last visit or last treatment, whichever is later, for participants without Visit 16 ²	Categorical descriptives

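### The readable SAP gives the TEAE summary by onset interval only the full-arm denominator, so with dropout or incomplete interim follow-up a constant risk would appear to decline

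*SAP*

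**What the plan says.** The TEAE row of SAP Table 5-20 (section 5.1.1.4.2) includes a summary by "SOC, PT, and AE onset time intervals", with five intervals: under 3, 3 to <6, 6 to <9, 9 to <12, and 12 months or more. The lead-in sets unit and population: "Unique participants reporting AEs in the following AE categories will be summarized by treatment group for the Safety Population as follows". The only method named is Categorical descriptives, which is M2 in Table 5-2 (section 5.1.1.1.3).

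M2 reports number and percentage. A participant with at least one "qualifying event counted once per individual category" contributes once to that category. An N1 is shown only when the denominator differs from the "number of participants in the population (standard percentage denominator"), and the one N1 defined is "N1 = participants with non-missing baseline value", which does not fit adverse events.

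TEAE observation ends at Visit 16. Without Visit 16, an event "more than 30 days after the last visit or last treatment, whichever is later", is no longer treatment-emergent (Table 5-19).

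SAP 5.1.1.6 runs every non-efficacy analysis at the interim. Table 5-17 separately counts participants completing 3, 6, 9 and 12 months, but Table 5-20 does not refer to it. Protocol 7.3.2.1 plans counts and percentages of TEAEs and no patient-time rate. The SAP Introduction notes: "Specifications of tables, figures, and data listings are contained in a separate document".

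**The concern.** Sex or age group is a property of the participant, so the denominator of a subgroup summary follows from the subset. Onset interval is a property of the event. Nothing in the row subsets participants by interval, so M2's default puts the whole arm under each interval. A participant who left in month 5 then counts as event-free from month 6 on. At the interim, so does a participant enrolled only five months earlier.

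The trial's objective (Protocol 2.1) is safety and tolerability over one year, and this is the readable summary that shows whether adverse events change with time on study. A decline produced by the denominator could be read as improving tolerability, and a real late increase could be masked.

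**Working it through.** The plan states no figure for this summary, so there is none to reproduce. What follows is an illustration under stated assumptions.

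**Inputs from the documents.** Arm size 400 (SAP 4.1: "Approximately 1200 patients will be randomized (400 patients per arm")). Treatment lasts 52 weeks (day 364), with safety follow-up four weeks later (day 392). Intervals are taken as days 0–90, 90–180, 180–270, 270–360 and 360–392, using the 90-day steps and day 360 of Table 6-4. Protocol 8.8 expects participants who discontinue to return four weeks after their last treatment-period visit, so observation is taken to continue 28 days after exit.

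**Assumed.** Constant event hazard λ; exponential dropout with share D gone by day 360, so μ = −ln(1 − D)/360; a participant may be counted again in each interval.

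**Formulas.** The fraction observed is S(t) = 1 to day 28, then exp(−μ(t − 28)). For an interval from a to b:
- full-arm percentage = ∫ λ·exp(−λ(t − a))·S(t) dt
- percentage of those entering = the same, divided by S(a)
- rate = expected TEAEs / patient-years

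**Worked case: D = 25%, risk 20% per 90 days.** λ = −ln(0.8)/90 = 0.002479; μ = −ln(0.75)/360 = 0.000799; λ + μ = 0.003278; λ/(λ + μ) = 0.756.
- Months 0 to <3: (1 − e^(−28λ)) + e^(−28λ) × 0.756 × (1 − e^(−62 × 0.003278)) = 0.0671 + 0.9329 × 0.756 × 0.1839 = 0.197.
- Months 9 to <12: S(270) = e^(−242μ) = 0.824; 0.824 × 0.756 × (1 − e^(−90 × 0.003278)) = 0.824 × 0.756 × 0.2555 = 0.159.
- Ratio 0.159/0.197 = 0.81.

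| | 0–<3 | 3–<6 | 6–<9 | 9–<12 | ≥12 |
|---|---|---|---|---|---|
| Full arm (400), % | 19.7 | 18.4 | 17.1 | 15.9 | 5.8 |
| Under observation at start, N | 400 | 381 | 354 | 330 | 307 |
| % of those | 19.7 | 19.3 | 19.3 | 19.3 | 7.5 |
| TEAEs per patient-year | 0.91 | 0.91 | 0.91 | 0.91 | 0.91 |

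**Range over dropout.** Full-arm ratio of months 9 to <12 to months 0 to <3: 1.00 at 0%, 0.93 at 10%, 0.81 at 25%, 0.69 at 40%. It is practically the same for 5% or 20% risk.

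**Table 5-17 counts as denominator.** In the same 25% case, completers at days 90, 180 and 270 number 372, 346 and 322. The four percentages become 19.7, 19.8, 19.8 and 19.8, which is equally flat.

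**First-onset counting.** If a participant counts only at the first onset of a term, the percentages fall even over those under observation: 19.7, 15.5, 12.4 and 9.9.

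**Last interval.** 392 − 360 = 32 days. With the number under observation as denominator it shows 0.36 to 0.38 of the first interval; only the rate makes it comparable.

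**Interim.** Illustration without dropout: both trigger counts are just met (300 at 6 months, 200 at 12), and K randomized ubrogepant participants meet the two-migraine condition and have the same entry pattern as the rest. The fraction who have reached month 0, 6 and 12 is 1, 300/K and 200/K, taken as linear between. The mean fraction observed is (3 + 300/K)/4 in months 0 to <3 and 225/K in months 9 to <12. For K = 800: 0.281/0.844 = 0.33. K = 600 gives 0.43, 400 gives 0.60, 300 gives 0.75. If the trigger is exceeded the dilution is smaller: 0.81 with 400 past 6 months and 300 past 12, of 400. With K = 800 and 5% risk per interval, the full arm shows 4.2, 2.7, 1.7 and 1.4%; the number entering gives 4.2, 3.9, 4.6 and 4.5%, because follow-up is cut inside intervals; the rate is 0.21 per patient-year throughout.

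**The case against.** The strongest reply is that the full-arm reading is an inference. M2 allows a different N1, other bullets in the same row also state no denominator, and the table specifications may set one. Text just before the section on adverse event groups is redacted. This stands as a limit: the point concerns what the readable SAP states, not what the tables will show.

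A reader might infer that a constant risk must appear to fall under this plan. The documents do not support that. With no dropout, complete follow-up and re-counting, the four 3-month intervals are flat, and no dropout rate is given. At 10% dropout the fall is small (19.9% to 18.4% in the 20% risk case). A reader might also infer that the comparison with usual care is biased; within an interval that needs retention to differ between arms, which the documents do not show.

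Table 5-17 already gives counts from which a reader can approximate the numbers remaining, and the interim includes it. That is right, and those counts serve well enough as a denominator. They do not correct the short last interval or interim follow-up cut inside an interval.

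Finally, a number at risk does not help if participants count only at first onset. A Table 5-20 footnote counts a participant once per preferred term for severity and causality, and no rule is given for onset intervals. This objection holds, so the counting rule has to be part of the fix.

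**Conclusion.** The point holds for the readable text: the only applicable denominator is the full arm, and no patient-time rate is attached to the onset-interval summary. The size of the apparent decline rests on assumed dropout: the 9 to <12 month percentage is about 0.93, 0.81 or 0.69 of the first for 10, 25 or 40%, given constant hazards and re-counting. The interim figures (0.33 to 0.75 at a just-met trigger) show that dilution can be larger, but they depend on an assumed entry pattern and cannot be fixed from the documents. Only the low value in the last interval needs no dropout assumption. The table is descriptive, counts are shown and no test depends on it. This is a cheap improvement, not a flaw that threatens the trial's conclusions.

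**What to change.** For the onset-interval summary in Table 5-20, at both the interim and the final analysis:

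1. State that a participant is counted once per SOC and PT within each interval in which a TEAE starts, and so may count in more than one interval.
2. Show, for each interval and arm, the number entering it and use that as the percentage denominator. The Table 5-17 counts at 3, 6, 9 and 12 months are an adequate basis; participants still under TEAE observation on the interval's first day are an alternative.
3. Add TEAEs per patient-year of observation in each interval, labelled as an event rate because its unit is events rather than participants. Read time trends from this column, including the short last interval.

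The third item is the essential one. The cost is a small derivation of patient-time and one added column, with no new data; late-interval percentages become somewhat higher. If the table specifications already do this, one sentence in the SAP closes the point.

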5.6 Treatment Regimen and Dosing

5.6.1 Ubrogепant

Table 2 presents the treatments that will be administered in this study. Patients randomized to the ubrogепant arms will be instructed to take 2 tablets to treat their migraine attack regardless of the dose group to which they are assigned.

Table 2 Treatments Administered for Initial and Optional Second Dose

Drug/Dose	Dose Frequency	Route of Administration	Investigational Product Administered	
			Initial Dose	Optional Second Dose
Ubrogепant 50 mg	Up to 8 times/4 weeks for 1 year (with optional second dose – maximum 16 times/4 weeks)	Oral (tablet)	Ubrogепant 50 mg/ placebo 50 mg	Ubrogепant 50 mg/ placebo 50 mg
Ubrogепant 100 mg	Up to 8 times/4 weeks for 1 year (with optional second dose – maximum 16 times/4 weeks)	Oral (tablet)	Ubrogепant 50 mg/ ubrogепant 50 mg	Ubrogепant 50 mg/ ubrogепant 50 mg

Patients randomized to the ubrogепant arms will be allowed to treat up to 8 qualifying migraine headaches (of any pain severity) per 4-week period throughout the course of a year. Patients will be instructed to treat the migraine headaches as soon as possible when all of the following conditions are met:

- At least 48 hours since the last dose of ubrogепant
- At least 48 hours of pain freedom (ie, no headache for at least 48 hours)
- The migraine headache started less than 4 hours ago
- The migraine headache is not already resolving on its own
- Prohibited medication has not been taken

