Number of attacks treated with study treatment per month ¹	
 ≥ 8 ≥ 6 and < 8 ≥ 4 and < 6 ≥ 2 and < 4 < 2 	Treatment period	Categorical descriptives
Average number of attacks treated with study treatment per month ¹	
For all participants:
 
 ≥ 8 ≥ 6 and < 8 ≥ 4 and < 6 ≥ 2 and < 4 < 2 
Subgroup analyses:
 
 by Sex by Age Group: <40 vs ≥40 by Age Group: <65 vs ≥65 by Race White vs All other races by CV risk category by renal function class 	Treatment period	Categorical descriptives
Maximum number of attacks treated with study treatment per	
 ≥ 8 ≥ 6 and < 8 ≥ 4 and < 6 	Treatment period	Categorical descriptives

Parameter	Description	Timing	Methodology
month, defined as maximum of monthly total number attacks treated with study treatment among months 1-12 for each participant ¹	
 • ≥ 2 and < 4 • < 2 		
Number of months with the number of attacks treated with study treatment in each category ¹	For each category: 
 • ≥ 8 • ≥ 6 and < 8 • ≥ 4 and < 6 • ≥ 2 and < 4 • < 2 	Treatment period	Categorical descriptives
Average number of study treatment taken per month ¹	
 • ≥ 16 • ≥ 14 and < 16 • ≥ 12 and < 14 • ≥ 10 and < 12 • ≥ 8 and < 10 • ≥ 6 and < 8 • ≥ 4 and < 6 • ≥ 2 and < 4 • < 2 	Treatment period	Categorical descriptives

Analysis visits defined in Section 6.2.2.

¹ Participants in the ubrogapant treatment arms only. No imputation for the last incomplete month.

Treatment compliance for this study will be summarized as follows:

Table 5-18 Treatment Compliance Summaries

Parameter	Description	Timing	Methodology
Overdosing ¹	Participants who took more than 2 doses within 48 hours or 2 calendar days (if time information is not available)		Listing

¹ Participants in the ubrogapant treatment arms only.

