6.2.2 Safety

The safety analysis visit windows for 3-month time interval are defined as follows:

Table 6-4 Safety Analysis Visit Definitions for 3-Month Time Interval

Analysis Phase	Analysis Visit (Derived)	Window
Treatment	Completed 3 months	Treatment Day \geq 90
	Completed 6 months	Treatment Day \geq 180
	Completed 9 months	Treatment Day \geq 270
	Completed 12 months	Completing treatment period per disposition CRF, or discontinued after day 360

Table 6-5 Safety Analysis Visit Definitions for 1-Month Time Interval

Analysis Phase	Analysis Visit (Derived)	Window
Treatment	Months 1	Treatment Day [1, 30]
	Months 2	Treatment Day [31, 60]
	Months 3	Treatment Day [61, 90]
	Months 4	Treatment Day [91, 120]
	Months 5	Treatment Day [121, 150]
	Months 6	Treatment Day [151, 180]
	Months 7	Treatment Day [181, 210]
	Months 8	Treatment Day [211, 240]
	Months 9	Treatment Day [241, 270]
	Months 10	Treatment Day [271, 300]
	Months 11	Treatment Day [301, 330]
	Months 12	Treatment Day [331, end of treatment period]

The analysis visit windows for safety endpoints are defined as follows:

Table 6-6 Safety Analysis Visit Definitions

Analysis Phase	Analysis Visit (Derived)	Scheduled Study Visit (eCRF)	Window
Pretreatment	Baseline	Baseline from Lead-in Study	Treatment Day \leq 1
	Week 4	(Visit 3) Week 4	Treatment Day [2, 42]
	Week 8	(Visit 4) Week 8	Treatment Day [43, 70]
	Week 12	(Visit 5) Week 12	Treatment Day [71, 98]
	Week 16	(Visit 6) Week 16	Treatment Day [99, 126]
	Week 20	(Visit 7) Week 20	Treatment Day [127, 154]
	Week 24	(Visit 8) Week 24	Treatment Day [155, 182]
	Week 28	(Visit 9) Week 28	Treatment Day [183, 210]
	Week 32	(Visit 10) Week 32	Treatment Day [211, 238]
	Week 36	(Visit 11) Week 36	Treatment Day [239, 266]
	Week 40	(Visit 12) Week 40	Treatment Day [267, 294]
	Week 44	(Visit 13) Week 44	Treatment Day [295, 322]
	Week 48	(Visit 14) Week 48	Treatment Day [323, 350]
	Week 52	(Visit 15) Week 52/Early Termination	Treatment Day [351, end of treatment period]

Analysis Phase	Analysis Visit (Derived)	Scheduled Study Visit (eCRF)	Window
	Safety Follow-up	(Visit 16) 4 Week Safety Follow-up	Treatment Day [end of treatment period+1, the last study visit]
	End of study	Final or termination visit	Latest non-missing assessment after randomization date

Safety follow-up visit will be presented in analysis tables for clinical laboratory values and vital signs.

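### TEAEs by frequency of use appear to be grouped on a treatment-period average that includes use after the event, which weakens a real use-harm gradient and can create a false protective one

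*SAP*

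**What the plan says.** - **SAP 5.1.1.4.2, Table 5-20 (TEAEs row).** TEAEs are summarized by "SOC, PT, and average number of migraine attacks treated with study treatment per month". The rows are at least 2, at least 4, at least 6 and at least 8. They are nested, and there is no row below 2. Events are counted "From randomization date to Visit 16 for participants with Visit 16, or within 30 days after last visit or last treatment", whichever of the last two is later. The averaging period is not defined here.
- **SAP 5.1.1.4.1, Table 5-17.** "Average number of attacks treated with study treatment per month" is listed with the treatment period as its timing, in disjoint bins that include one below 2. The only further rule is "No imputation for the last incomplete month".
- **SAP 6.2.2, Table 6-5** ("Safety Analysis Visit Definitions for 1-Month Time Interval"). Months 1 to 11 have 30 days each. Month 12 is "Treatment Day [331, end of treatment period".
- **Related displays.** TEAEs by 3-month onset interval are a separate summary, not crossed with use. Exposure is listed attack by attack. Dosing times are set against results over time only in the patient plots for ALT or AST of at least 3 times ULN (SAP 5.1.1.4.3).
- **Protocol 5.6.1.** Patients "will be allowed to treat up to 8 qualifying migraine headaches (of any pain severity) per 4-week period", so use is elective below that ceiling.

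**The concern.** The grouping variable is measured after randomization and keeps accruing after the event it is meant to explain. An event in month 3 is filed partly by use in months 4 to 12. If the event makes a patient treat fewer attacks with ubrogepant, it lowers its own exposure category.

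The protocol leaves room for this. Other acute migraine medication is allowed within limits (4.5.1.1), and lack of a qualifying event is a reason for discontinuation only after 6 months without a treated qualifying migraine (8.8). A patient can therefore use little drug for a long time and remain in the table.

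Frequency of use matters in this study: the interim analysis is triggered by patients averaging at least 2 treated migraines per month (Protocol 7.6, SAP 5.1.1.6). In the readable text this is the only TEAE table that addresses it, so a flat result could be taken as reassurance. The bias acts in one direction, toward hiding harm.

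**Working it through.** The plan states no figure on this point, so there is none to reproduce.

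**1. Hand arithmetic on the 12-month average** = (rate before × months before + rate after × months after) / 12.

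- 8 per month for 3 months, then an AE and 1 per month for 9 months: (24 + 9)/12 = 2.75. The event arose at 8 per month but counts only in the row of at least 2.
- 4 per month for 3 months, then 1 per month: (12 + 9)/12 = 1.75. The patient is in no row.
- Ceiling: 8 per 4 weeks × 13 = 104 attacks, or 104/12 = 8.67 per month. The top row needs 8 × 12 = 96, which is 92% of the maximum, so a small reduction empties it.

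**2. Simulation of the SAP's nested rows** (400,000 patients per scenario, to separate bias from chance). Apart from the ceiling, every input is an assumption: intended use gamma with mean 4 per month and shape 2.5, capped at 8.67; 12-month AE risk of about 30% (common) or 5% (rare) at 4 attacks per month; hazard ratio (HR) per extra monthly attack of 1.0, 1.1 or 1.2; a stated share of affected patients cut use and stay; 5% withdraw and are averaged over their own time on treatment.

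Percent with the AE, rows ≥2 / ≥4 / ≥6 / ≥8:

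| Scenario | Common AE | Rare AE |
|---|---|---|
| HR 1.1, by pre-event use | 32.1 / 35.6 / 39.6 / 42.5 | 5.6 / 6.4 / 7.3 / 7.9 |
| HR 1.1, 10% halve use | 31.7 / 34.7 / 38.1 / 40.1 | 5.6 / 6.1 / 6.9 / 7.4 |
| HR 1.1, 25% halve use | 31.1 / 33.3 / 35.6 / 36.4 | 5.4 / 5.8 / 6.2 / 6.4 |
| HR 1.1, 50% halve use | 30.2 / 30.7 / 30.7 / 29.0 | 5.2 / 5.3 / 5.3 / 4.7 |
| HR 1.1, 50% cut by three quarters | 28.1 / 27.7 / 28.5 / 28.0 | 4.8 / 4.6 / 4.6 / 4.2 |
| HR 1.2, by pre-event use | 34.2 / 41.4 / 49.7 / 56.4 | 6.2 / 7.8 / 9.8 / 11.6 |
| HR 1.2, 50% halve use | 32.6 / 36.5 / 39.7 / 41.4 | 5.8 / 6.6 / 7.1 / 6.9 |
| No relation, by pre-event use | 30.1 / 30.0 / 30.1 / 30.2 | 5.2 / 5.2 / 5.2 / 5.1 |
| No relation, 50% halve use | 27.9 / 25.2 / 22.5 / 19.2 | 4.8 / 4.2 / 3.6 / 2.9 |

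Top row minus bottom row, common AE, HR 1.1: 42.5 − 32.1 = 10.4 points by pre-event use; 8.4 at 10% (81% kept); 5.3 at 25% (51% kept); −1.2 at 50%. For HR 1.2 with 50% halving, 41.4 − 32.6 = 8.8 of 22.2 points remain (40%). With no relation and 50% halving, a false fall of 8.7 points appears.

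**3. Test of two remedies.** Assumed monthly hazard 0.03 × exp(0.12 × attacks per month), that is 3.0 per 100 patient-months at zero use and 0.03 × exp(0.12 × 8.67) = 8.5 at the ceiling. Use is gamma with mean 3.6, and nobody changes use. Rates per 100 patient-months, from the bin below 2 to the bin of at least 8:

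- Table 6-5 months, with event months counted only up to onset and event-free months in full: 8.1 falling to 1.4. The true relation is reversed. With no relation, the same rule gives 5.8 falling to 0.5.
- Preceding 30 days, applied to all time at risk alike: 3.7 rising to 7.2, and flat at 3.0 with no relation. The slope is somewhat shallow because a 30-day count measures a patient's use with noise.

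**The case against.** Several objections stand.

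- **The averaging period is inferred.** Table 5-20 does not define it. It comes from an exposure table, table specifications sit in a separate document, and parts of the SAP's derivation text are not readable.
- **The cut-down rate is unsupported.** The documents give no figure for it. Near-complete loss needs about half of affected patients to halve their use with a modest true relation.
- **Early withdrawal does little harm here.** Patients who leave at the AE keep their pre-event average if they are averaged over their own time on treatment, although the SAP does not spell this out.
- **The table is descriptive and not alone.** No test is attached. Onset intervals, attack-level exposure listings, maximum monthly use and, for the liver, plots with dosing times are also planned.

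A reader might infer that patients with AEs are moved into low-use rows. The rows are nested, so they stay in the lower rows and leave the higher ones, or leave the table below 2. A reader might also infer that the table will show a flat or protective pattern for this drug, or that the safety comparison of 50 mg with 100 mg is compromised. The first rests wholly on an assumed response. The second does not follow, because that comparison uses randomized groups and not this average.

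What remains is that no visible rule keeps post-event use out of the classification, and that the resulting bias has a known direction.

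**Conclusion.** The point holds as a directional bias of uncertain size, provided Table 5-20 uses the treatment-period average of Table 5-17. If 10% to 25% of affected patients halve their use, the relation is weakened: about 80% to 50% of the top-to-bottom difference survives for a common AE at a hazard ratio of 1.1. Loss or slight reversal needs about half of them to halve use, or to cut further. A stronger true relation is reduced but still visible for a common AE. With no true relation, the same behaviour yields a false protective trend. These figures rest on the assumed use distribution, risks and responses listed above.

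The consequence is confined to one descriptive table. This is a cheap improvement to the plan and does not call the study's main safety comparison into question.

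**What to change.** 1. State in SAP 5.1.1.4.2 over which period, and with which denominator, the average in Table 5-20 is taken.
2. Add a table of first TEAE onsets per 100 patient-months, by ubrogepant dose, in the disjoint Table 5-17 bins including the one below 2. Classify every day or month at risk, with or without an event, by attacks treated in the preceding 30 days, or in the preceding full Table 6-5 month. End each patient's time at risk at the first onset of the term concerned.
3. Do not cut only the event months at onset. That measures cases over a shorter window than non-cases and pushes events into the low-use bins even when nobody changes use.
4. Give the first 30 days a separate row, because no full preceding window exists, and state how time after the end of treatment is handled.
5. Keep the whole-period table as supportive, with a footnote that it includes use after the event.

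The cost is one extra derivation from dosing dates already collected, and rates in place of simple percentages. Use before onset is still not randomized, so the new table remains descriptive.
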